2.0 BACKGROUND AND SIGNIFICANCE

2.1 Background of Medical Need

Patients with hematologic malignancy are particularly vulnerable to functional decline due to anemia, resulting in an increased risk of functional dependence, falls, chemotherapy induced-toxicity and mortality.¹ Historically, patients were advised to abstain from physical activity due to chemotherapy-induced immune suppression and fatigue resulting in further physical deconditioning. In recent years, the perspective on physical activity has changed significantly in cancer patients, and many reports document the benefit of exercise in the cancer patient population.²⁻⁴ Physical fitness is highly predictive of survival,⁵ yet gauging physical fitness remains a challenge for oncologists and we lack interventions to help this population maintain and/or regain their fitness successfully. Many factors are not modifiable in patients with blood cancer, such as age of diagnosis, genetics of disease, comorbidities, or response to therapy; however exercise is an intervention that can be implemented with a broad range of therapeutic effects. Oncologists require objective assessment of fitness and introducing the physiologic aging biomarker, p16, is potentially practice chap1nging for clinicians to objectively gauge fitness for treatment and/or transplant. This proposal is the first to compare

a biomarker of aging (p16) with baseline physical performance metrics and the first to explore if exercise can improve p16 transcript expression.

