2.3 Molecular biomarkers are associated with aging, frailty, and physical inactivity

Advances in biomarkers of aging can improve upon subjective measures and better quantify physiologic age. Recently, investigators have refined the ability to quantify biologic age by use of a molecular marker, p16. p16 is a tumor suppressor protein that inhibits cell cycle progression, promotes cellular senescence, and has been associated with frailty phenotypes, physical inactivity, and age related comorbidities.¹² p16, originating from the *INK4/ARF* locus on chromosome 9p21, belongs to a family of cyclin-dependent kinase (CDK) cell cycle inhibitors and prevents cell cycle progression by blocking CDK4/6 dependent phosphorylation of the retinoblastoma tumor suppressor (Rb).¹³ Prolonged expression of p16

promotes irreversible cell cycle arrest or cellular senescence. p16 tumor suppressor levels increase exponentially with chronologic aging across most mammalian species including humans.^{14,15} Beyond age, p16-induced senescence can be triggered by variety of internal stressors including DNA damage, replication errors, telomere erosion, and reactive oxygen species.¹⁶ External stressors can also trigger p16 expression such as physical inactivity, chemotherapy, and tobacco exposure. Additionally, single nucleotide polymorphisms located near the INK4/ARF locus are linked with age-related diseases including cardiovascular disease, diabetes and decreased physical function.¹⁷⁻¹⁹ Therefore, it is believed that p16 levels reflect a physiologic age or fitness. Recently Liu and colleagues demonstrated a means of quantifying this molecular marker of age in peripheral blood T-cells,²⁰ providing a feasible and relatively non-invasive strategy to monitor p16 expression over time in a clinical setting to predict treatment tolerance and guide clinical decision making. In this research proposal, we focus on the most validated biomarker (p16) however, we are also exploring immunosenescence of aging (T-cell subpopulations, CD28 expression), markers of energy, and epigenetic markers (DNA methylation, miRs). Additional biomarkers of aging and an immunosenescence panel will be collected and explored.

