3.2 Patient Selection Inclusion Criteria

- Patients with hematologic malignancy receiving care (chemotherapy, immunotherapy, targeted agents, bone marrow transplant, or other) for their hematologic malignancy at the Ohio State University.
- Age ≥ 60 years
- Impairments in physical function, as defined by a score ≤ 9 on the SPPB pre-screen
- Medical clearance from an oncologist or primary care physician stating the participant is able to participate in an unsupervised, moderate-intensity physical activity program
- Ability to understand and the willingness to sign a written informed consent document

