4.5.5 Exercise Intervention: Otago Exercise Programme (OEP)

Exercise interventions are an established method of improving physiologic and functional performance in older adults. The structured OEP focuses on strengthening, balance retraining, and walking. OEP requires minimal training and can be provided by any physical therapist. OEP requires patient engagement and takes approximately 30 minutes three times weekly, with walking twice weekly. All physical therapist engaged in the protocol are OEP certified. The OEP is 8 physical therapy visits over 4 months. Participants will record daily of walking, exercise and falls in an exercise journal [APPENDIX J].

Patients may require more than 2 sessions monthly of physical therapy according to the physical therapist prescribed recommendations. In this event, exercise logs and fall diaries will be collected at their 1st and 3rd visit monthly. Patients will be reimbursed for their travel at these two visit times only (see Section 5.8).

Table 1. Otago	o Exercise Programme (OEP)				
	Strengthening	Balance Retraining	Walking		
Assessment			Timed Up and Go		
Activity	Five leg muscle strengthening exercises Four levels of difficulty	Twelve balance retraining exercises Four levels of difficulty	Advice about walking		
Intensity	Moderate Challenge 8-10 repetitions before fatigue	Moderate Challenge Each exercise at a level the patient can safely perform	Usual pace with usual walking aid		
Progressions	Increases from one to two sets Increase amount of ankle weight after 2 sets of 10	Supported exercise and unsupported exercise	Walk indoors Advance to walking outdoors when strength and balance have improved		
Length of Exercise Sessions	Approximately 30 minutes total for exercises; Exercises can be divided up over the day		30 minutes; can be split into three 10 minute walks throughout the day		
Home Based Frequency	3 times a week	At least 3 times a week	Twice a week		
Duration	Physical therapy (8 visits, twice monthly, until transplant or 4 months) Transplant physical therapy consult (twice weekly physical therapy consult during transplant admission). Home based exercise throughout their 6 month enrollment.				

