6.3 Correlative Analysis

Presence of deleterious genes and p16 pre-OEP and post-OEP will be correlated with clinical factors (age, performance status, adherence to OEP), GA profiles, SPPB scores.

Serum studies evaluating mRNA will be characterized and analyzed in relation to functional assessment outcomes as well as clinical outcomes of interest. microRNA measures will be assessed in relation to cytokine measures using graphical analyses and measures of correlation. FDR corrections will be utilized to correct for the simultaneous comparisons of the multiple markers.

Quantified p16 expression pre and post OEP will be described, and independently analyzed in relationship to functional assessment outcomes such as GA scales, SPPB Scores as well as

clinical outcomes of interest (age). In addition, p16 expression will be evaluated in relation to clinical outcomes, such as tolerance of OEP, adherence of OEP, length of hospitalization and readmissions in a descriptive manner. Generalized linear models will be used similar to those described above to assess the impact of p16 expression on GA scores depending on data completeness. Spearman rank correlation coefficients will be used in relation to continuous measures (e.g. age), two-sample tests (Wilcoxon rank sum tests) will be used for comparing p16 expression between two groups (e.g. incidence of del17), and Kruskal-Wallis tests will be used to compare p16 expression between more than two groups. Descriptive statistics and graphical analyses will be used to evaluate p16 expression within each of the groups to better understand potential trends of interest.

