7.4 Feasibility Preliminary Data: Recently, investigators have evaluated the impact of lifestyle on PBTL *p16* expression in healthy volunteers.⁵⁸ The authors reported that modifiable factors such as exercise, smoking, and body mass have an age-independent impact on *p16* expression where physical exercise duration showed an inverse association with the level of *p16* T-cell mRNA expression ($r^2=0.1922$, p<0.0001). This suggests that exercise may

exert protective effects in age-dependent accumulation of senescent cells. External factors such as chemotherapy also impact p16 expression. In preliminary data, we identified that BMT also significantly increases the expression of T-cell p16 mRNA expression in patients with multiple myeloma pre- and post-transplant (90 day). As such, we aim to explore if exercise alters p16 expression.

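### The p16 analysis names no term or stratum for chemotherapy or transplant given between samples, so an exercise effect on p16 cannot be separated from a treatment effect

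*Combined protocol and SAP*

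**What the plan says.** **Aim.** Section 2.1 presents the study as "the first to explore if exercise can improve p16 transcript expression". Section 7.4 repeats the aim directly after naming treatment as a cause of p16 change.

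**Other causes of p16 change.** Section 2.3: "External stressors can also trigger p16 expression such as physical inactivity, chemotherapy, and tobacco exposure". Section 7.4: "External factors such as chemotherapy also impact p16 expression", and, in multiple myeloma, from before transplant to 90 days after it, "BMT also significantly increases the expression of T-cell p16 mRNA expression".

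**Exposure.** Section 3.2 admits patients "receiving care (chemotherapy, immunotherapy, targeted agents, bone marrow transplant, or other) for their hematologic malignancy". Section 3.6 describes one exercise cohort of at most 100, with no concurrent control.

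**Timing.** Section 7.3 takes blood for p16 before the OEP, after it and at 6 months. Table 1 in section 4.5.5 gives the duration as "Physical therapy (8 visits, twice monthly, until transplant or 4 months"). Section 4.1 places transplant after the outpatient physical therapy (PT) appointments.

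**Analysis.** Section 6.3: "Quantified p16 expression pre and post OEP will be described". It relates p16 to age, performance status, OEP adherence and tolerance, geriatric assessment (GA), SPPB, length of hospitalization and readmissions. It names no chemotherapy or transplant term, stratum or sensitivity analysis. Section 7.3 adds a comparison with an age-matched dataset from which only age is retrieved.

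**The concern.** The protocol identifies a competing cause of p16 change, enrols only patients likely to be exposed to it, and then names no way of accounting for it. In a single cohort, the before-after difference is the sum of everything that happened between the two samples. If treatment raises p16 while exercise lowers it, a flat result could mean no exercise effect or two effects that cancel, and a rise could be taken as harm. Section 6.2 says the findings need validation in a larger multicenter trial. A p16 change that cannot be attributed gives that trial little to build on.

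**Working it through.** **1. The plan's own figure.** There is none for p16. The only power statement (section 6.2) is for SPPB: 30 pairs, effect 0.55 SD of the differences, two-sided signed rank test, at least 80% power. With alpha 0.05 (assumed, as none is stated), a paired t-test has 82.9% power, and the signed rank test at relative efficiency 3/π has 81.1%. The figure reproduces, but it says nothing about p16.

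**2. Does any planned analysis separate treatment from exercise?**
- Description of p16 before and after the OEP (6.3): no split by treatment is named.
- Correlations with clinical factors (6.3): treatment is not among those listed.
- Generalized linear models (6.3): p16 is the predictor and GA the outcome, so p16 change is not modelled.
- Transplant subgroup (6.2): covers falls, readmission, length of stay, GA, SPPB and PROMIS, but not p16.
- Age-matched dataset (7.3): supplies only age, so it cannot adjust for treatment.

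**3. Which treatment falls in which interval?** PT stops at transplant or at 4 months, so the post-OEP sample should fall near or before transplant. Transplant can precede that sample through the windows: Table 2 allows 30 days around the visit plus 14 for the biomarker (44 if they add), and Table 3 allows 45 days around the visit. The myeloma finding is at 90 days after transplant, which fits the 6-month sample better. Section 6.3 specifies no analysis of p16 change to 6 months. Chemotherapy can fall in either interval.

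**4. Size of the bias.** Let e be the exercise effect, f the share exposed between samples and d the upward shift, in SD of p16 change. The expected pooled change is e + f·d. The documents give none of these, so f = 0.2 to 0.3 and d = 0.5 to 1.5 are assumptions. With e = 0:

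| f | d | bias f·d | SD of change, √(1 + f(1−f)d²) |
|---|---|---|---|
| 0.2 | 0.5 | +0.10 | 1.02 |
| 0.2 | 1.5 | +0.30 | 1.17 |
| 0.3 | 0.5 | +0.15 | 1.03 |
| 0.3 | 1.5 | +0.45 | 1.21 |

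If a two-sided 5% paired t-test were applied, noncentral-t rejection rates would be 8% to 28% (f = 0.2) and 12% to 50% (f = 0.3) with 30 pairs, or 14% to 62% and 25% to 91% with 80 pairs. At f = 0.05 they are 5% to 7% and 6% to 10%. Section 6.3 plans no such test for p16 change, so these only show scale. For chemotherapy f could be well above 0.3: at f = 1 the bias is d itself.

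**5. Hiding a benefit.** A true fall of 0.55 SD (borrowed from the SPPB statement) is cancelled when f·d = 0.55, for example 55% exposed with a shift of 1 SD. In simulation with 30 pairs and a signed rank test, the chance of detecting that fall drops from 81% with no treatment effect to 63% (f = 0.2, d = 0.5), 42% (0.4, 0.5) and 10.5% (0.4, 1.0).

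**6. Adherence correlation.** If transplant both raises p16 and cuts PT visits short, p16 change and adherence become negatively correlated with no exercise effect. Simulating 30 patients with f = 0.4, d = 1 and adherence 1 SD lower in the exposed gives a mean Spearman correlation of −0.19. A significant negative result occurs in 17% of runs (nominal 2.5%). Over f = 0.2 to 0.4, d = 0.5 to 1.0 and an adherence deficit of 0.5 to 1.5 SD, the range is 4% to 28%. The direction depends on scoring: footnote c of Table 2 also counts inpatient visits, which a transplant stay could increase.

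**The case against.** The strongest reply is that this is an exploratory correlative in a feasibility study. The p16 change is only to be described, the primary endpoint is untouched, and section 6.3 leaves room for comparing p16 between groups, with del17 given only as an example. Treatment data are collected under section 5.4. All of this is true, and it limits the weight of the point. It does not remove it, because exploring whether exercise alters p16 is a stated aim and no planned analysis addresses the cause that the protocol itself names.

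Four stronger readings are tempting and are not supported:
- A reader might infer that transplant is the main problem in the pre/post-OEP contrast. Sections 4.1 and 4.5.5 place it mostly after the PT visits. The evidence that it raises p16 is from myeloma only, with no magnitude.
- A reader might infer that treatment will be mistaken for an exercise benefit. The shift is upward and a benefit would be a fall. In the 30-pair model of step 4, with 20% to 30% exposed, a false significant fall has probability 0.7% or less, below the nominal 2.5%. A false benefit could arise only by a side route such as the adherence correlation.
- A reader might take the rejection rates as error rates of the plan. They belong to an unplanned test under assumed inputs.
- A reader might infer that a no-transplant stratum or a treatment-adjusted visit effect would isolate exercise. Those patients are still receiving care, the visit effect still carries time and disease course, and selecting on a post-baseline event changes who is compared.

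**Conclusion.** The concern holds as a limit on what the p16 aim can conclude. As planned, the pooled p16 change cannot separate exercise from treatment, and the likely error is a hidden benefit or apparent harm. This rests on the protocol's own statements and needs no numerical assumption. Chemotherapy is the main confounder between the pre- and post-OEP samples, transplant chiefly of the 6-month sample, and the adherence correlation may also be affected.

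The size is not known. The range of +0.10 to +0.45 SD of change rests wholly on assumed exposure (20% to 30%) and shift (0.5 to 1.5 SD). It would be smaller with little exposure and larger if most patients receive chemotherapy that raises p16. The remedy is a cheap improvement to a correlative analysis; feasibility is unaffected.

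**What to change.** In section 6.3:
1. Report p16 change on the log scale for each interval (pre- to post-OEP, and post-OEP to 6 months), separately for patients with and without transplant, and with and without cytotoxic chemotherapy, in that interval. Use the treatment data already collected under section 5.4 and give the numbers in each group. If nearly all patients received chemotherapy, say so.
2. As an exploratory analysis, if data allow, fit a mixed model for log p16 over the three samples with visit, age and time-varying indicators for transplant and chemotherapy. Examine the adherence correlation within the no-transplant group.
3. State that neither the no-transplant stratum, the adjusted visit effect nor the age-matched dataset isolates exercise, and limit any statement about exercise and p16 to hypothesis generation.

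This changes analysis wording only and needs no new visits, samples or patients. The price is smaller strata and wider intervals.

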7.5 Obtaining samples

Peripheral blood will be obtained by clinic staff for mRNA, miRNA, and cytokine studies. Samples will be obtained in clinical space (currently on HTC and 5th floor James, as examples).

Specifically, approximately 30ml of peripheral blood will be collected into phlebotomy tubes: up to 10ml in purple top EDTA tubes and 20ml in serum separator tubes.

7.6 Sample processing

Sample pick up and processing will be performed in the Leukemia Tissue Bank using the following general procedure for cryopreservation of serum and plasma.

To obtain the plasma the blood collected in EDTA coated tubes will be transferred to 50 ml sterile tube and centrifuged at 1800 rpm for 10min at room temperature. The supernatant (plasma) will be collected and stored at -80°C for further studies. The cellular pellet will be gently re-suspended in PBS to reach 2X the original volume (for 10ml of plasma 20ml PBS) and then stratified in 1X of Ficoll-Paque. This will be centrifuged at room temperature for 20 min at 2000 rpm. The white ring containing monocytes, T- and B- lymphocytes will be removed and washed with FBS enriched culture media. The tube will be centrifuged at 1200 rpm at room temperature for 6 min. The cellular pellet will be resuspended in 90% FBS and 10% DMSO and placed in cryo-tubes at -80°C and after 3 days will be placed in liquid nitrogen for long-term storage.

For the serum collection the tubes will be centrifuged at 2,200-2,500 rpm for 15 min and the serum will be stored at -80°C.

To obtain T cells: Whole blood collected in a purple top EDTA tube will be divided into two equal volume portions, approximately 5mL each. RosetteSep Human T Cell Enrichment Cocktail (Stem Cell Technologies # 15061) will be added to each tube at a ratio of 50uL per mL of whole blood. Tubes will be mixed by inversion and incubated for 20 minutes at room temperature. Next, samples will be diluted in an equal volume of phosphate buffered saline containing 2% fetal bovine serum (PBS/2%FBS). Diluted samples will be gently mixed and then carefully layered on top of Histopaque 1077 density medium (Sigma-Aldrich #10771) in a 50mL conical tube. The amount of density medium used will equal the original blood aliquot volume (~5mL). Tubes will then be centrifuged at 1200xg for 20 minutes at room temperature with the centrifuge brake set to 'off'. Following separation, enriched T-cells will be removed from the plasma interface using a pipette and placed into a fresh 15mL conical tube. The cells will be washed by adding PBS/2%FBS to the tubes until they are filled to the top fill line. Tubes will then be centrifuged at 400 x g for 4 minutes at room temperature with maximum brake. The resulting supernatant will be removed with a pipette and transferred to a 1.5 mL microcentrifuge tube. This sample will be centrifuged at 400 x g for 4 minutes at room temperature with maximum brake. The resulting supernatant will be carefully and completely removed using a pipette. The remaining T-cell pellet will be stored in a -80 $^{\circ}$ freezer until processing.

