7.0 CORRELATIVE ANALYSIS / SPECIAL STUDIES

7.1 Overview

Peripheral blood will be obtained for mRNA, miRNA, and flow cytometry analysis. While specific details of the processing, extraction, and analysis are included in this protocol, these details may change with innovations in laboratory techniques and hence are considered general guidelines only.

7.2 p16 Aging Biomarker: Identifying candidacy for treatment or transplant is generally subjective and is dependent on age, performance status, and comorbidities. The clinical need for objective quantitative measures of physiologic fitness remains unmet. As such, *p16*, a marker of cellular senescence, represents an attractive proxy for physiologic age and may be an additional tool in the clinical evaluation. Many investigations are focusing on biomarkers of age to weigh treatment options and gauge toxicity.⁵⁶ We aim to capture physiologic fitness and with use of *p16* expression in peripheral blood T-lymphocytes (PBTL). The molecular biomarker, *p16^{INK4a} (p16)* is an established marker of systemic cellular senescence associated with physiologic aging. *p16* expression increases ~16-fold over an individual's lifetime and can be readily measured in PBTL.⁵⁷

7.3 Correlative Analysis Procedures: Patients enrolled have peripheral blood collected for p16 analysis serially at three time points 1) pre-OEP 2) post-OEP and 3) 6 months. Peripheral blood will be obtained in EDTA coated tubes (10 ml) where CD3+ T-cells will be isolated using RosetteSep Reagents. RNA will be extracted using RNeasy Plus Mini Kit (Qiagen), and analyzed using reverse-transcription real-time quantitative PCR for p16, ARF, and standard housekeeping genes. p16 mRNA expression will be compared to an age-matched control dataset. The source of this dataset is a primary analysis study previously conducted by the PI, [name] (IRB protocol number 2014C0008). The only information retrieved from this control dataset will be age; no protected health information will be collected. The full dataset has been de-identified and the study team does not have access to identifiable information about this population.

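### Section 7.6 moves the wash supernatant, not the cell pellet, into the tube from which the T-cell pellet for p16 is later stored (wrong as written, minor severity)

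*Combined protocol and SAP*

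**What the plan says.** The T-cell paragraph of section 7.6 (Sample processing) runs in this order after the density-gradient separation:

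- The cells are collected: "enriched T-cells will be removed from the plasma interface using a pipette and placed into a fresh 15mL conical tube".
- They are washed: "The cells will be washed by adding PBS/2%FBS to the tubes until they are filled to the top fill line".
- They are spun: "Tubes will then be centrifuged at 400 x g for 4 minutes at room temperature with maximum brake".
- One fraction is moved on: "The resulting supernatant will be removed with a pipette and transferred to a 1.5 mL microcentrifuge tube".
- That tube gets a second spin at the same force, time and brake setting, and then: "The resulting supernatant will be carefully and completely removed using a pipette".
- The product is frozen: "The remaining T-cell pellet will be stored in a -80" degree freezer.

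Section 7.7 extracts T-cell RNA from cell pellets, and section 7.8 measures p16 on the T-cell mRNA so obtained. Section 7.1 qualifies the laboratory text as a whole: "these details may change with innovations in laboratory techniques and hence are considered general guidelines only".

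**The concern.** A wash spin separates cells from wash fluid: the cells go to the bottom and the fluid is the supernatant. The plan carries the fluid forward and says nothing more about the pellet. The closing sentence then treats the second tube as if it held the T-cells. Both statements cannot be right.

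The step matters because p16 is measured on this material. Section 1.3 lists p16 under the secondary objectives, section 2.1 pairs it with the SPPB as a predictive measure in the study's main purpose, section 6.3 analyses it before and after the exercise programme, and section 7.3 collects it at three time points. Section 7.5 allows up to 10 mL of EDTA blood, and section 7.6 divides it into two portions of about 5 mL, so T-cell isolation can use the whole EDTA draw and no T-cell reserve is described. Staff who follow the sentence and staff who infer its intent would also store different material under the same label.

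**Working it through.** The plan gives no figure to reproduce here. The check is a trace of which fraction is carried forward, a volume comparison, and a ceiling on the number of samples.

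**Trace of the fractions (section 7.6)**

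1. Before the wash, the T-cells are in the 15 mL tube.
2. After the wash spin, they are in the pellet of that tube. This assumes that the spin brings down most of the cells. The plan relies on the same idea, because its second spin, at the same force and time, is what forms the pellet to be stored.
3. The fraction moved to the 1.5 mL tube is the supernatant. Nothing is said about the 15 mL pellet, neither that it is kept nor that it is thrown away.
4. After the second spin, any pellet in the 1.5 mL tube can come only from cells that stayed in the wash fluid.
5. That pellet is what is stored, and it is called the T-cell pellet.

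Steps 3 and 5 conflict. The documents give no recovery rate, so the shortfall can be described only as few T-cells and not as a percentage.

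**Comparison within the same section.** The plasma and mononuclear-cell procedure in section 7.6 also has a wash spin. There the pellet is the fraction that is resuspended and frozen. The T-cell paragraph departs from that pattern without giving a reason.

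**Volume**

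- Input: a 15 mL tube filled to its top line. The exact volume is not stated; 14 to 15 mL is assumed.
- Ratio to the receiving tube: 14 / 1.5 = 9.3 and 15 / 1.5 = 10.
- If each of the two blood portions has its own tube: 2 × 14 = 28 mL to 2 × 15 = 30 mL of supernatant.

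The supernatant cannot be transferred as described. A small resuspended pellet could be. This points to a drafting slip in which the sentence on the pellet was lost or misworded.

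**Ceiling on samples.** Section 3.6 sets a maximum of 100 patients and section 7.3 sets three collections: 100 × 3 = 300. This assumes full recruitment, no attrition and every sample mishandled, so it is an upper bound and not an expected loss.

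**The case against.** The strongest reply is that nobody could carry out the sentence, so nobody would be misled by it. The volume mismatch would show at the first sample. The closing sentence of the paragraph, the parallel procedure and section 7.7 all point to the pellet. The team also appears to have run this assay before: section 7.3 cites a p16 control dataset from an earlier study by the principal investigator, and section 7.4 reports preliminary T-cell p16 results in myeloma patients before and after transplant. Much of this stands. It makes systematic loss unlikely, and it is why the severity is minor.

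The section 7.1 caveat helps less. It allows for change as techniques improve. It does not say which of two conflicting statements in the current text applies.

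Three stronger readings are tempting, and the documents do not support them:

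- *The protocol tells staff to discard the T-cells.* It does not. The pellet is left unaccounted for; loss would follow from literal execution and is not instructed.
- *Up to 300 p16 measurements would be lost.* That figure is only the ceiling. Nothing in the documents shows that any sample was handled in this way.
- *A failed sample would go unnoticed and could never be replaced.* Section 7.7 assesses RNA concentration and quality, and section 7.8 includes controls for T-cell purity (CD3G) and RNA quantity (YWHAZ), so a nearly cell-free sample should show up. Table 2 allows biomarker collection within 14 days either side of the visit, and section 7.6 also freezes mononuclear cells, which include T-lymphocytes.

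These safeguards have limits. Pellets stay frozen until processing, so a failure may be found after the redraw window has closed. The only action limit stated in section 7.7 is the 260/280 ratio, with no minimum yield. With at most 10 mL of EDTA blood, both cell fractions may not be available from one draw.

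**Conclusion.** The step is wrong as written. It carries forward the supernatant, later stores a T-cell pellet from the same tube, and leaves the pellet that holds the cells unmentioned; no other section corrects this. Read literally, the stored sample would hold few T-cells for the p16 assay. That conclusion assumes that the wash spin pellets most of the cells; the volume argument assumes a fill of 14 to 15 mL.

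The severity is minor. The intent can be recovered from the surrounding text, the assay controls should reveal failed samples at processing, and the number of samples affected is unknown and may be zero. The primary endpoint in sections 1.4 and 6.1 is completion of the exercise programme, and no p16 result enters it or the eligibility criteria.

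**What to change.** Reword the one sentence in section 7.6 so that, after the wash spin, the supernatant is removed and the cell pellet is resuspended and transferred to the 1.5 mL tube. The second spin and the steps after it can stay as they are. The documents give no medium or volume for this resuspension and do not say whether the two blood portions are pooled, so the laboratory should confirm these details against its working procedure before the text is changed.

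If samples have already been stored, the laboratory should confirm which fraction went into the 1.5 mL tube, ideally before the p16 assay is run, so that any unusable sample is identified in advance.

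The cost is one sentence and one query to the laboratory. No endpoint, visit or analysis changes.
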